## 5.1.5. Administration of Study Drug

Study drug will be dispensed to subjects at the clinical site in appropriately labeled tubes.

Subjects will take the tubes home and self-administer study drug (or have caregiver apply if necessary), except on clinic visit days (when study drug is applied under supervision at the site), to affected areas once daily.

Subjects will be instructed to apply study drug as follows:

- Once daily application to affected areas; subjects are to choose the application time they prefer and to apply the study drug at that approximate time each day of study participation.
- If a subject misses a daily dose, it will be recorded as a protocol deviation. The subject should continue dosing the next day and should not apply more than once daily to make up for the missed dose on the previous day.
- If chosen application time is in the evening, the dose should be applied at least 30 minutes prior to bedtime.
- Study drug should be applied to dry, clean skin.
- Wash hands after application, unless treating lesions on the hands or fingernails.
- Study drug should be applied to all lesions, including newly appearing lesions and lesions that have improved during the study.
- Subjects are allowed, but not required, to treat fingernails, toenails, palms, soles, and scalp lesions with study drug; however, efficacy analyses will not include assessment of improvement of psoriasis in these areas. If using study drug on the scalp, no other treatment for scalp psoriasis is permitted during the study.
- If there is residual cream visible on the disease-affected lesional skin, then the subject should be instructed to continue to lightly rub the cream into the skin until it is no longer visible.
- If study drug is applied to the subject by another person, that person should thoroughly wash his/her hands after application. When possible, use of disposable gloves is recommended.
- Subjects should record the time of study drug application in the daily diary.
- Subjects should avoid swimming, bathing, showering, or strenuous activities for at least 2 hours after application of study drug.
- On clinic visit days, study drug should be applied in the clinic under the supervision
  of site personnel and after safety and efficacy assessments have been completed
  NOTE: The time of the dose and assessments on clinic visit days will depend on the
  time of the clinic visit. Therefore, the timing of the clinic visit may differ from the

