## 5.4. Compliance with Study Drug Administration

At baseline, study staff will provide the subject with detailed instructions concerning protocol requirements and use of study drug. Additionally, subjects will be asked to complete a daily diary with the time of each application of study drug. At each post baseline study visit, study staff will review use of study drug, as applicable, with the subject.

When subjects are dosed at the site, they will apply the study drug under supervision of the study staff. The date and time of each dose administered in the clinic will be recorded in the source documents. The study drug and study subject identification will be confirmed at the time of dosing by a member of the study site staff other than the person dispensing the study drug.

At the time of dispensing study drug to each subject, site personnel will weigh the tubes to be dispensed and will record the weight of all tubes dispensed at each visit in the drug accountability logs. Subjects will be instructed to bring all used and unused tubes with them to each study visit. Site personnel will weigh the returned tubes (used and unused) and record the weight in the drug accountability logs. If a tube has been lost, discarded, or forgotten by the subject, then the site personnel will make a notation of this on the drug accountability logs. The site personnel will remind the subject to keep all tubes of study drug dispensed and to bring all used and unused tubes to each clinic visit. These data will be used to estimate subject compliance with use of study drug. Tubes of study medication dispensed at the most recent prior visit which remain unopened (the foil cap on the tube remains fully intact/undisturbed) may be re-dispensed to study subjects at the current visit. Opened, partially used tubes or tubes with foil overlay removed are not to be re-dispensed to study subjects. If there is any question as to re-dispensation, sites should issue new tubes of study medication to the subject(s).

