		
 
Updated exclusion criteria to specify use of
 

		oral corticosteroids
		• Section 9 Handling of Missing Data:
		
 
Clarified baseline PGA score and baseline
 

		value of the corresponding endpoint are
		included in multiple imputation model
		
 
Updated the example SAS code for multiple imputation
 

		
 
Section 11.4 Analysis Visit Window:
 

		
 
Updated analysis visit window for Week 12 and Week 16
 

		• Section 12.4 Study Exposure and Compliance:
		
 
Renamed the parameter "number of days
 

		actually dosed" to "number of doses
		administered"
		• Section 12.7.4 Functional Outcomes and Health-
		related Quality of Life Endpoints:
		
 
DLQI: Added texts for handling of missing
 

		data in domain scores
		SF-36: Removed physical component score
		and mental component score; Added 8 domain
		scores.

• Section 12.8 Efficacy Analyses:

o Added percent change from baseline for peak

Date Reason for update Section Updated

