### 8. ANALYSIS POPULATIONS

The following populations are defined:

- Safety population: All randomized subjects who receive at least 1 application of study drug will be included in the Safety population. Subjects will be analyzed as treated.
- Intent-to-treat (ITT) population: All randomized subjects will be included in the Intent-to-treat population. Subjects will be analyzed as randomized.
- Per Protocol (PP) population: All subjects in the ITT population who did not have any major protocol deviations or other events that may impact the interpretation of the primary efficacy endpoint will be included in the PP population. Exclusion criteria for the PP Population may include:
  - o Failure to meet the enrollment inclusion/exclusion criteria
  - On-study use of oral corticosteroids for >3 days and/or at >10mg dose
  - Failure to have a Week 12 assessment that occurs <=3 days post last dose and also between study day 78 to 91 (inclusive) for the primary efficacy endpoint. Alternative days post dose and visit window may be used upon review of the actual blinded data before database lock.

• Failure to be compliant with treatment regimen (as defined in Section 12.4, i.e., compliance < 80%)

Additional criteria that may or may not be documented as protocol deviations may be added to determine PP population. The composition of the PP population will be determined and documented in blind reviews of the database conducted prior to unblinding the study database.

The ITT and PP Populations will be used for the analyses of efficacy endpoints. The ITT population is considered as the primary population for efficacy analyses and the PP will be considered as supportive. If a subject receives an incorrect study treatment other than the intended study treatment, the analysis of that subject's data will be based on the actual treatment received for the safety and PP analyses and the randomized assignment for the ITT analyses. If a subject receives more than 1 study treatment, the treatment group assignment for the safety and PP analyses will be determined on a case by case basis.

• Pharmacokinetic (PK) population: All subjects who undergo plasma PK sampling and have evaluable concentration-time data for analysis will be included in the PK population. A sample that is below the limit of quantification (BLQ) of the assay is considered evaluable.

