### 12.4 Study Medication Exposure and Compliance

The following exposure and compliance parameters will be summarized descriptively by treatment group:

• Total number of days exposed, defined as date of last dose of study drug minus date of first dose of study drug plus 1.

- Number of doses administered, calculated from the subject dose diary. If a subject does not return diary or returns the diary with missing dosing record, the number of doses taken during that period is assumed to be 0.
- Grams (g) of study drug administered, total and average per day. Drug administered is calculated as the summation of the difference between dispensed weight and returned weight for all returned tubes. Unreturned tubes will be assumed unused and will be included as 0 gram in amount drug used calculation.
- Percent compliance will be calculated as the number of doses administered over the number of days exposed.
- Subject compliance, defined as ≥80% compliance over the entire duration of study. If the percentage of study medication compliance is unknown, the subject is assumed to be non-compliant with study medication.

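### Percent compliance in SAP 12.4 counts doses rather than dosed days, so a second application recorded on one day can offset a missed day in the 80% test

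*SAP*

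**What the plan says.** SAP 12.4 builds compliance from two quantities. The numerator is "Number of doses administered, calculated from the subject dose diary", with unreturned or incomplete diaries counted as zero doses for the period. The denominator is "Total number of days exposed, defined as date of last dose of study drug minus date of first dose of study drug plus 1". The ratio is then defined: "Percent compliance will be calculated as the number of doses administered over the number of days exposed". The only limit is a lower one: "Subject compliance, defined as ≥80% compliance over the entire duration of study". No upper limit, truncation at 100% or one-per-day rule appears anywhere in the SAP.

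SAP 8 lists, among criteria that may exclude a subject from the Per-Protocol population, "Failure to be compliant with treatment regimen (as defined in Section 12.4, i.e., compliance < 80"%).

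On the protocol side, treatment is once daily for 12 weeks. Protocol 5.1.5 has each missed daily dose recorded as a protocol deviation and says that the subject "should not apply more than once daily to make up for the missed dose on the previous day". Protocol 5.4 describes the source record: "subjects will be asked to complete a daily diary with the time of each application of study drug".

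**The concern.** The numerator counts applications and the denominator counts days. Under a once-daily regimen the two match only if no day holds more than one application. If a diary does hold two on one date, the ratio credits the second against a day without treatment. That is the make-up dosing which Protocol 5.1.5 tells subjects to avoid.

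Two outputs are exposed. One is the compliance summary by arm. The other is the 80% criterion that may be used to form the Per-Protocol population, in which the primary and secondary endpoints are repeated as supportive analyses. A subject with too few treated days could stay in a population meant to reflect the regimen as prescribed, and a subject applying more often than once daily would be scored as fully compliant.

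**Working it through.** The plan gives no compliance figure to reproduce, so the check applies the SAP 12.4 formula directly.

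**Inputs**
- Days exposed, D: 12 weeks × 7 = 84 as the worked case (treatment duration, SAP 6). D = 82, 85 and 87 are also checked, because actual exposure varies with visit timing.
- Threshold: at least 80% (SAP 12.4 and SAP 8).
- d = days with at least one recorded application; e = extra applications beyond the first on any day. The documents give no value for e, so it is varied.

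**Formulas**
- SAP ratio = (d + e) / D
- Day-based ratio = d / D
- Difference = e / D. At D = 84, each extra application adds 1/84 = 1.2 percentage points.

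**Threshold.** 0.80 × 84 = 67.2, so 68 doses are needed. With one dose per day that allows 84 − 68 = 16 missed days.

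**Results at D = 84**

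| Days dosed (missed) | Extra applications | Day-based ratio | SAP ratio |
|---|---|---|---|
| 68 (16) | 0 | 68/84 = 81.0%, passes | 68/84 = 81.0%, passes |
| 67 (17) | 1 | 67/84 = 79.8%, fails | 68/84 = 81.0%, passes |
| 60 (24) | 8 | 60/84 = 71.4%, fails | 68/84 = 81.0%, passes |
| 57 (27) | 11 | 57/84 = 67.9%, fails | 68/84 = 81.0%, passes |
| 34 (50) | 34 | 34/84 = 40.5%, fails | 68/84 = 81.0%, passes |
| 84 (0) | 84 | 84/84 = 100%, passes | 168/84 = 200%, passes |

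The 34-day row is the outer bound if no day holds more than two applications. The 67-day row is the realistic one: near the threshold, a single extra application changes the classification. The last row shows that there is no upper limit.

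**Other exposure lengths.** The doses needed are 66 for D = 82 (0.80 × 82 = 65.6), 68 for D = 85 (0.80 × 85 = 68) and 70 for D = 87 (0.80 × 87 = 69.6). One dosed day short of the threshold gives 65/82 = 79.3%, 67/85 = 78.8% and 69/87 = 79.3%. One extra application lifts these to 80.5%, 80.0% and 80.5%, so the conclusion does not depend on D = 84.

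**The case against.** **The diary form is not shown.** If it has a single application field per date, doses equal dosed days and the problem cannot arise. Protocol 3.1 and 5.1.5 speak of the application time in the singular, and the SAP revision history describes the move from days dosed to doses administered as a renaming, which could mean that the two were taken as the same quantity. This stands as a condition on the point. It does not settle the matter, because Protocol 5.4 refers to the time of each application and the SAP text would count every one recorded.

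**Other safeguards exist.** Each missed dose is a protocol deviation, so the 67-day subject would carry 17 and the 57-day subject 27. Diaries are reviewed at the clinic visits and grams used are summarised by arm. SAP 8 also allows exclusion for major deviations and for criteria added at blinded review. A reader might infer that the 80% figure alone decides Per-Protocol membership. The documents do not support that: it is one criterion that may be applied. However, none of the other routes names over-application, and tube weights do not enter the compliance percentage.

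**Overstatement is not established.** A reader might infer that mean compliance is overstated. That holds only if extra applications occur, and other rules pull the other way: missing diary records count as zero, and the Schedule of Assessments has visit-day applications recorded in the clinic rather than in the home diary. If only the diary is read, up to four supervised doses (Day 1 and Weeks 2, 4 and 8) could go uncounted, which is 4/84 = 4.8 percentage points. The net direction is unknown.

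**Doses taken over doses expected is a recognised measure.** True, but without a daily limit it does not measure adherence to a once-daily schedule.

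**Conclusion.** The point holds as a conditional defect in a definition. As written, the ratio lets an extra recorded application offset a missed day, and at 84 days one such application is enough to move a subject with 67 dosed days from 79.8% to 81.0%. It rests on one assumption that the documents do not confirm, namely that the diary or case report form can hold more than one application on a date. The number of subjects affected cannot be estimated, and the error is zero if no such day exists.

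The reach is limited to the compliance summary and one possible exclusion criterion for the supportive Per-Protocol analyses. A reader might infer a threat to the efficacy conclusions. There is none: the primary analysis and the fixed-sequence tests rest on the ITT population with multiple imputation, and none of them uses compliance. This is a minor correction, worth making because it is cheap and because a pre-specified rule should match the regimen instead of relying on blinded review to notice the exception.

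**What to change.** In SAP 12.4, define percent compliance as the number of calendar days from first to last dose with at least one recorded application, taken from the diary or from the clinic record on visit days, divided by the number of days exposed. The ratio then cannot exceed 100%. Summarise days with more than one application by arm, and list those subjects for the blinded Per-Protocol review. The 80% threshold and SAP 8 can stay as they are.

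The cost is a sentence or two in the SAP, a small change to the derivation and one added summary and listing. The dates and times are already collected. The downside is that reported compliance may be slightly lower if extra applications occurred. If none did, removing the double count changes nothing.

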#### 12.5 Prior and Concomitant Medications

Prior (within the 34 days before Visit 1 and with stop dates prior to first dose of study drug) and concomitant (ongoing or with stop dates on or after first dose of study drug) medications will be listed by subject for each treatment group. If the medication is ongoing or the stop year is missing, the medication will be considered as received for the entire duration of the study. Medications will be coded using WHO-DD terminology.

To distinguish prior vs concomitant medications, the following rules for stop dates will apply:

- If only year was recorded, and it is before Baseline, it is a prior medication; if year is same or after Baseline, it is assumed to be a concomitant medication.
- If day is missing, but month and year are before Baseline, it is a prior medication; if month and year are the same as Baseline, it is assumed to be a concomitant medication; if month and year are after Baseline, it is a concomitant medication.
- If start date is after Baseline, it is a concomitant medication regardless.

Prior and concomitant medications will be summarized separately by treatment, WHO-DD Anatomical-Therapeutic-Chemical (ATC) classification and preferred term (PT).

### 12.6 Medical History and Concurrent Procedures

Medical history (including previous and ongoing medical conditions) will be coded using MedDRA and listed by subject. Medical history will be summarized by system organ class (SOC) and PT for each treatment.

Psoriasis History, Cardiovascular Risk Factors and Liver Disease Family History will be summarized and listed by subject separately.

The following will be summarized by treatment group for psoriasis history:

- Duration (year) of disease, defined as year of Screening visit minus year of initial psoriasis diagnosis. Duration of disease will be reported as <5, 5-10, and >10 years for summary purpose.
- Area affected (scalp, pam, fingernails, toenails, soles)

### 12.7 Efficacy Endpoints

### 12.7.1 Primary Efficacy Endpoint

The primary efficacy endpoint is the proportion of subjects who achieve a Physician Global Assessment (PGA) treatment response, defined as a PGA score of clear (0) or almost clear (1) with a minimum 2-grade improvement from Baseline at Week 12.

The PGA is a static 5-point assessment of overall disease severity, as determined by the Investigator, ranging from 0 (clear) to 4 (severe).

### 12.7.2 Secondary Efficacy Endpoints

The secondary endpoints are:

- Proportion of subjects with ≥ 75% improvement in Psoriasis Area and Severity Index from Baseline (PASI-75) at Week 12
- Proportion of subjects with a PGA score of 0 or 1 at Week 12
- Mean change in percent of total body surface area (%BSA) affected from Baseline to Week 12
- Proportion of subjects with ≥90% improvement in PASI score from Baseline (PASI-90) to Week 12.

The PASI score assesses the severity of psoriasis taking into account the overall severity of erythema (redness), induration (plaque thickness), and scale, and the extent of %BSA affected with psoriasis. The 3 clinical signs are each graded on a 5-point scale (0 to 4) and the %BSA affected is scored on a 7-point scale (0 to 6) for each of the 4 specified body regions (head, upper extremities, trunk, and lower extremities). The individual scores are multiplied by a weighted factor for each body region; the sum of these scores gives the overall PASI score.

### 12.7.3 Exploratory Efficacy Endpoints

The exploratory endpoints to further characterize the efficacy of tapinar of cream, 1% compared with vehicle control over time are:

- Time (days) to achieving a PGA treatment response, defined as days from date of first dose until achieving a PGA score of 0 or 1 with a minimum 2-grade improvement from Baseline. Subjects who have no PGA response will be censored at the date of their last PGA assessment.
- Proportion of subjects with a PGA score of 0 or 1 at Weeks 2, 4, and 8
- Proportion of subjects who achieve a PGA treatment response at Weeks 2, 4, and 8
- Mean absolute and percent change in PASI score from Baseline to Weeks 2, 4, 8, and 12
- Proportion of subjects with ≥ 50% improvement in PASI score (PASI-50) from Baseline to Weeks 2, 4, 8, and 12
- Proportion of subjects with ≥ 75% improvement in PASI score (PASI-75) from Baseline to weeks 2, 4, and 8
- Proportion of subjects with ≥ 90% improvement in PASI score (PASI-90) from Baseline to weeks 2, 4, and 8
- Mean change in %BSA affected from Baseline to Weeks 2, 4, and 8
- Mean % change in %BSA affected from Baseline to Weeks 2, 4, 8, and 12.

### 12.7.4 Functional Outcomes and Health-related Quality of Life Endpoints

To describe the effect of tapinar fcream, 1% on functional outcomes and the associated impact on daily activities and attitudes in adults with plaque psoriasis:

- Change in Peak Pruritus-Numeric Rating Scale (Peak Pruritus-NRS) from Baseline at Weeks 2, 4, 6, 8, 10, 12 and 16
- Change in psoriasis impact on daily activities, as measured by the Dermatology Life Quality Index (DLQI) total and individual dimension scores from Baseline at Weeks 4, 12, and 16

**The DLQI** is a 10-item PRO measure that assesses the extent to which the skin condition has affected the subject's quality of life over the past week, including 6 domains (daily activities, personal relationships, symptoms and feelings, leisure, work/school, and treatment). The total score (0-30) will be calculated as the sum of 10 questions with each ranging from 0 to 3. The scoring of each question is as follows:

Very much	Scored 3
A lot	Scored 2
A little	Scored 1
Not at all	Scored 0
Not relevant	Scored 0

Question unanswered	Scored 0
Question 7: "prevented work or studying"	Scored 3

If one question is left unanswered this is scored 0 and the scores are summed and expressed as usual out of a maximum of 30. If two or more questions are left unanswered the total DLQI score is missing. If question 7a is answered 'yes' or 'not relevant', then the answer of 7b will be ignored.

When summarizing the domain scores, if a domain contains two questions and the answer to one of the questions is missing, that domain will be scored as the answer to the non-missing question. If all the answers to questions in a domain are missing, the domain will not be scored.

- Change in psoriasis symptoms, as measured by the Psoriasis Symptom Diary (PSD), including total and 16 individual scores from Baseline at Weeks 2, 4, 8, 12, and 16.
  - PSD is a 16-item assessment measures self-reports of psoriasis symptoms, and impact on functional health. The total score will be calculated as the sum of 16 questions with each ranging from 0 to 10. If any of the 16 questions is unanswered, the total score will be considered as missing.
- Change in the eight domain scores, as measured by the RAND Short Form-36 (SF-36) questionnaire from Baseline at Weeks 4, 12, and 16.

The 8 domain scores below will be computed using the scoring rules for the RAND 36-Item Health Survey (Version 1.0):

- Physical functioning
- o Role limitations due to physical health
- o Role limitations due to emotional problems
- o Energy/fatigue
- o Emotional well-being
- Social functioning
- o Pain
- General health

